# 7.3.7. Surgical and Minimally-Invasive/Non-surgical Interventions for BPH

At Visit 2 (Baseline) and each scheduled 13 week clinic visit post-randomization, the investigator will record in the designated section of the eCRF any BPH-related prostatic surgery and/or any minimally-invasive/non-surgical procedures undergone by the subject during his participation in the study (see Appendix 4 for a glossary of prostatic surgical and minimally-invasive/non-surgical interventions.).

Any resected tissue from patients undergoing prostatic surgery during the study should be sent to the local pathology laboratory for routine histopathology analysis. Information including the date of surgery, reason for surgery and histology results (including high grade prostatic intraepithelial neoplasia (HGPIN) diagnosis and Gleason score, if prostate cancer diagnosis) will be collected and recorded in the eCRF, as applicable.

## 7.3.8. For-Cause Biopsy for Diagnosis of Prostate Cancer

TRUS-guided for-cause biopsies may be conducted at any time during a subject's participation in the study if, in the judgement of the investigator, there is a clinically significant medical trigger, such as:

- Adverse change in digital rectal exam
- Clinically significant increase in serum PSA
- Nodular areas suspicious detected on TRUS

Tissue from all for-cause biopsy cores will be sent to the local pathology laboratory for histopathology analysis.

For all subjects undergoing for-cause biopsy during the study, information including the date of biopsy, reason for biopsy, biopsy results, number of cores obtained, high grade prostatic intraepithelial neoplasia (HGPIN) diagnosis, and surgery outcome will be

collected and recorded in the eCRF, as applicable. In addition, for those subjects with a positive biopsy, information about prostate cancer, including date of diagnosis, Gleason score (classic scoring or modified scoring system) at biopsy and/or surgery, percentage of core involved (semi-quantification of volume of prostate cancer), cancer positive cores (reported as number of positive cores over total number of cores) will be collected and recorded in the eCRF.

## 7.3.9. Suicidality

Dutasteride is considered to be an active compound in human central nervous system (CNS) that may affect mood or behavior via effects on the CNS (directly or indirectly). A GSK review of published literature and clinical trial data for dutasteride has shown that dutasteride is not associated with an increased risk of suicidal thinking or behavior when given to this patient population.

There has been some concern that some CNS-active drugs may be associated with an increased risk of suicidal thinking or behavior when given to some subjects with certain conditions. Although these drugs and other similar drugs of the same class have not been associated with an increased risk of suicidal thinking or behavior when given to this patient population, GSK considers it important to monitor for such events before or during clinical studies with compounds such as this.

Subjects in Study ARI114265 will be assessed for suicidality and unusual changes in behavior using the Columbia Suicide Severity Rating Scale (C-SSRS). To protect subjects in the study, scores from C-SSRS tests will be reviewed in real time by the investigator and appropriate advice given to participants. Consideration should be given to discontinuing study treatments in subjects who experience signs of suicidal ideation or behavior. Refer to Section 7.4.6 for more information.

## 7.3.10. Collection of Other Efficacy Measures

At Visit 2 (Baseline) each scheduled 13 week clinic visit, the investigator will record in the designated section of the eCRF defined incidences of urinary tract infection/urosepsis, urinary incontinence, and renal insufficiency the subject experiences during his participation in the study.

#### 7.4. Adverse Events

The investigator or site staff will be responsible for detecting, documenting and reporting events that meet the definition of an AE or SAE as outlined in Section 7.4.1 and Section 7.4.2.

#### 7.4.1. Definition of an AE

Any untoward medical occurrence in a subject or clinical investigation subject, temporally associated with the use of a medicinal product, whether or not considered related to the medicinal product.

Note: An AE can therefore be any unfavorable and unintended sign (including an abnormal laboratory finding), symptom, or disease (new or exacerbated) temporally associated with the use of a medicinal product. For marketed medicinal products, this also includes failure to produce expected benefits, abuse, or misuse. Examples of events meeting the definition of an AE include:

- Any abnormal laboratory test results (hematology, clinical chemistry, or urinalysis) or other safety assessments (e.g., ECGs, radiological scans, vital signs measurements), including those that worsen from baseline, and felt to be clinically significant in the medical and scientific judgement of the investigator.
- Exacerbation of a chronic or intermittent pre-existing condition including either an increase in frequency and/or grade of the condition
- New conditions detected or diagnosed after study treatment administration even though it may have been present prior to the start of the study
- Signs, symptoms, or the clinical sequelae of a suspected interaction
- Signs, symptoms, or the clinical sequelae of a suspected overdose of either study treatment or a concomitant medication (overdose per se will not be reported as an AE/SAE) unless this is an intentional overdose taken with possible suicidal/self-harming intent. This should be reported regardless of sequelae)

"Lack of efficacy" or "failure of expected pharmacological action" *per se* is not to be reported as an AE or SAE. However, any signs and symptoms and/or clinical sequelae resulting from "lack of efficacy" will be reported as an AE or SAE, if they fulfill the definition of an AE or SAE

Events that **do not** meet the definition of an AE include:

- Any clinically significant abnormal laboratory findings or other abnormal safety assessments that are associated with the underlying disease, unless judged by the investigator to be more severe than expected for the subject's condition.
- Medical or surgical procedure (e.g., endoscopy, appendectomy); the condition that leads to the procedure is an AE.
- Situations where an untoward medical occurrence did not occur (social and/or convenience admission to a hospital).
- Anticipated day-to-day fluctuations of pre-existing disease(s) or condition(s) present or detected at the start of the study that do not worsen.
- The disease/disorder being studied, or expected progression, signs, or symptoms of the disease/disorder being studied, unless more severe than expected for the subject's condition.

#### 7.4.2. Definition of a SAE

A serious adverse event is any untoward medical occurrence that, at any dose:

Results in death

## b. Is life-threatening

NOTE: The term 'life-threatening' in the definition of 'serious' refers to an event in which the subject was at risk of death at the time of the event. It does not refer to an event, which hypothetically might have caused death, if it were more severe.

c. Requires hospitalization or prolongation of existing hospitalization

NOTE: In general, hospitalization signifies that the subject has been detained (usually involving at least an overnight stay) at the hospital or emergency ward for observation and/or treatment that would not have been appropriate in the physician's office or out-subject setting. Complications that occur during hospitalization are AEs. If a complication prolongs hospitalization or fulfils any other serious criteria, the event is serious. When in doubt as to whether "hospitalization" occurred or was necessary, the AE should be considered serious.

Hospitalization for elective treatment of a pre-existing condition that did not worsen from baseline is not considered an AE.

d. Results in disability/incapacity, or

NOTE: The term disability means a substantial disruption of a person's ability to conduct normal life functions. This definition is not intended to include experiences of relatively minor medical significance such as uncomplicated headache, nausea, vomiting, diarrhea, influenza, and accidental trauma (e.g. sprained ankle) which may interfere or prevent everyday life functions but do not constitute a substantial disruption.

- e. Is a congenital anomaly/birth defect.
- f. Medical or scientific judgement should be exercised in deciding whether reporting is appropriate in other situations, such as important medical events that may not be immediately life-threatening or result in death or hospitalization but may jeopardize the subject or may require medical or surgical intervention to prevent one of the other outcomes listed in the above definition. These should also be considered serious. Examples of such events are invasive or malignant cancers, intensive treatment in an emergency room or at home for allergic bronchospasm, blood dyscrasias or convulsions that do not result in hospitalization, or development of drug dependency or drug abuse.
- g. All events of possible drug-induced liver injury with hyperbilirubinaemia, defined as ALT ≥ 3xULN and bilirubin ≥ 2xULN (>35% direct) (or ALT ≥ 3xULN and INR>1.5, if INR measured) termed 'Hy's Law' events (INR measurement is not required and the threshold value stated will not apply to patients receiving anticoagulants.)

NOTE: bilirubin fractionation is performed if testing is available. If testing is unavailable, record presence of detectable urinary bilirubin on dipstick indicating direct bilirubin elevations and suggesting liver injury. If testing is unavailable and a subject meets the criterion of total bilirubin  $\geq 2xULN$ , then the event is still reported as an SAE. If INR is obtained, include values on the SAE form. INR elevations >1.5 suggest severe liver injury.

Other events that must be reported as Serious AEs in this study, regardless of satisfying criteria a-g, are:

- h. Male Breast Cancer
- i. Spontaneous Abortion in female partner of male subject (see Partner Pregnancy, Section 7.4.5)

## 7.4.2.1. Laboratory and Other Safety Assessment Abnormalities Reported as AEs and SAEs

Any abnormal laboratory test results (hematology, or clinical chemistry) or other safety assessments (e.g., ECGs, radiological scans, vital signs measurements), including those that worsen from baseline, and felt to be clinically significant in the medical and scientific judgement of the investigator are to be recorded as AEs or SAEs.

However, any clinically significant safety assessments that are associated with the underlying disease, unless judged by the investigator to be more severe than expected for the subject's condition, are **not** to be reported as AEs or SAEs

#### 7.4.2.2. Cardiovascular Events

Investigators will be required to fill out event specific data collection tools for the following AEs and SAEs:

- Myocardial infarction/unstable angina
- Congestive heart failure
- Arrhythmias
- Valvulopathy
- Pulmonary hypertension
- Cerebrovascular events/stroke and transient ischemic attack
- Peripheral arterial thromboembolism
- Deep venous thrombosis/pulmonary embolism
- Revascularisation

This information should be recorded in the specific cardiovascular eCRF within one week of when the AE/SAE(s) are first reported.

#### 7.4.2.3. Death Events

In addition, all deaths will require a specific death data collection tool to be completed. The death data collection tool includes questions regarding cardiovascular (including sudden cardiac death) and non-cardiovascular death.

This information should be recorded in the specific death eCRF within one week of when the death is first reported.

#### 7.4.2.4. Sentinel Events

A Sentinel Event is a GSK-defined SAE that is not necessarily drug-related but has been associated historically with adverse reactions for other drugs and is therefore worthy of heightened pharmacovigilance. Medical monitor review of all SAEs for possible Sentinel Events is mandated at GSK. The GSK medical monitor may request additional clinical information on an urgent basis if a possible Sentinel Event is identified on SAE review. The current GSK-defined Sentinel Events are listed below:

- Acquired Long QT Syndrome
- Agranulocytosis/Severe Neutropenia
- Anaphylaxis & Anaphylactoid Reactions
- Hepatotoxicity
- Acute Renal Failure
- Seizure
- Stevens Johnson syndrome/Toxic epidermal necrosis

# 7.4.2.5. Disease-Related Events and/or Disease-Related Outcomes Not Qualifying as SAEs

A disease-related event is an event generally associated with the disease under study and is not typically associated with the use of the investigational product. In this study, disease-related events will be captured as part of efficacy assessments and hence will be reported as AEs or SAEs only under the following circumstances:

- If a disease-related event is considered by the investigator to be more severe than expected for the subject's condition, but does not meet the definition of serious as outlined in Section 7.4.2, the event should be reported as an AE.
- If a disease-related event is considered by the investigator to be more severe than expected for the subject's condition and meets the definition of serious as outlined in Section 7.4.2, the event must be reported as an SAE.
- If a disease-related event is life-threatening or fatal, regardless of the investigator's assessment of severity expected for the subject's condition, the event must be reported as an SAE.

Disease-related events for this study are listed below.

- BPH symptoms (incomplete emptying, frequency, intermittency, urgency, weak stream, straining, nocturia)
- Changes in Qmax
- Changes in subject's response to questions asked in the IPSS and humanistic assessments.

- Acute urinary retention
- Urinary tract infection/urosepsis
- Urinary incontinence (overflow/urge)
- BPH-related Renal insufficiency

#### 7.4.3. QTc Events

If QTc events occur the investigator should promptly contact the medical monitor to receive advice on measures to be taken.

#### 7.4.4. Liver Events

If serious liver events occur the investigator should follow the standard serious event reporting process described in the protocol. For non-serious liver events that are clinically significant, the investigator will contact the medical monitor to receive advice on measures to be taken

## 7.4.5. Partner Pregnancy

As with other 5-alpha reductase inhibitors, dutasteride inhibits the conversion of testosterone to dihydrotestosterone and may, if administered to a woman carrying a male fetus, inhibit the development of the external genitalia of the fetus (see CIB). Small amounts of dutasteride have been recovered from the semen in subjects receiving dutasteride 0.5 mg per day. Based on studies in animals, it is unlikely that a male fetus will be adversely affected if his mother is exposed to the semen of a patient being treated with dutasteride (the risk of which is greatest during the first 16 weeks of pregnancy). Even though it is unlikely that a male fetus will be adversely affected if his mother is exposed to the semen of a partner being treated with dutasteride, some countries recommend the use of condoms in the local dutasteride labels. For these countries it is recommended that the patient avoids exposure of his partner to semen by use of a condom for 6 months after drug discontinuation.

#### 7.4.5.1. Time period for collecting partner pregnancy information

Pregnancy information should be collected on any female partner of a male study subject who is pregnant or becomes pregnant while the subject is participating in the study. All pregnancies in female partners of male subjects will be collected after the start of dosing until 6 months after the subject's last dose of study drug.

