## STUDY DESIGN

This is a multicentre, randomized, double-blind, parallel group study. The aim of the study is to investigate whether combination therapy with dutasteride and tamsulosin is more effective than tamsulosin monotherapy for improvement of symptoms and health outcomes in a population of men at risk of BPH clinical progression including older men ( $\geq$ 50yrs), with moderate-severe symptoms of BPH, enlarged prostates ( $\geq$ 30cc) and PSA $\geq$ 1.5ng/mL.

Subjects who provide informed consent will be screened for inclusion into the study and eligible subjects will receive placebo tamsulosin and placebo dutasteride for four weeks. Following the four-week single-blind, placebo run-in period, each subject will be randomized to one of the following two treatment groups, according to a pre-determined randomisation schedule (1:1 ratio) for the double-blind phase of the study:

- Dutasteride 0.5mg once daily + tamsulosin 0.2mg once daily
- Dutasteride placebo once daily + tamsulosin 0.2mg once daily

Subjects will self-administer the study medication once daily for up to 104 weeks (2 years). Subjects will return to the clinic at 13 week intervals post-randomisation during the 2 year treatment period (i.e. at 13, 26, 39, 52, 65, 78, 91, and 104 weeks), for the assessments listed in the Time and Events Schedule, Section 7.

The total study duration for each subject will be up to 110 weeks, involving 11 scheduled visits. Due to the circadian changes in urinary flow measurements in BPH subjects, study visits for an individual subject should be conducted consistently in either the morning or afternoon hours to assess all urinary flow measurements.

Every effort will be made to ensure that all randomized subjects complete study assessments. The investigator and site staff are reminded that the subject should make every effort to adhere to all scheduled protocol visits/procedures and their associated windows. In circumstances where this is not possible, e.g. subject is on holiday and is late/early or even misses a study visit, this should be documented in the subject notes with reasons. The investigator should make every effort to ensure the subject always has sufficient study medication between study visits. If visit windows associated with each visit are utilized, the next visit should be scheduled in line with the randomisation baseline visit (Visit 2).

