# 6.3. Treatment after Discontinuation of Study treatment or Discontinuation of Study

Post study treatment will not be provided as part of the protocol. Upon discontinuation from assigned study treatment, subjects may receive additional (non protocol) therapy at the discretion of the treating physician. The investigator is responsible for ensuring that consideration has been given to the post-study care of the patient's medical condition whether or not GSK is providing specific post-study treatment.

If a subject discontinues study treatment permanently after Visit 2 (post-randomisation) for any reason, other than lost to follow-up, the investigator should make every effort to complete the following activities listed below: (Note: the subject has the right to refuse any further contact for study-related follow-up information).

- End of Study Treatment Assessments as outlined in Section 7.2.2.5.
- Biannual follow-up for clinical events via telephone contact every 6 months relative to baseline visit (Visit 2) until the 2 year anniversary of randomisation. Any occurrence of death, AUR, BPH-related prostatic surgery or minimally-invasive/non-surgical intervention for BPH, prostate cancer /biopsy reported after premature withdrawal of study treatment, and outcomes of sexually related adverse events reported during the treatment period, should be fully documented in the eCRF and source documents. The purpose of the collection of these data is to more fully document study endpoints and related events.

No additional study activities other than those that are stated above are planned after a subject's permanent discontinuation from study treatment

A subject is considered a 'withdrawal' from the study when no study procedure has occurred, no follow-up has been performed and no further information has been collected for this subject from the date of withdrawal/last contact.

The primary reason for permanent discontinuation of study must be documented in the subject's medical records and eCRF.

Subjects who are withdrawn from the study after randomisation will not be replaced.

In the event that a subject is prematurely discontinued from the study treatment or withdraw from the study at any time due to an AE (as defined in Section 7.4.1, "Definition of an AE") or SAE (as defined in Section 7.4.2, "Definition of an SAE"), the procedures described in Section 7.4.7 ("AEs and SAEs") must be followed.

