#### Visit 1b (Placebo run-in)

Visit 1b should be conducted a maximum of 14 days after V1a (allowing sufficient time for lab results from V1a to be returned to site).

- 1. Review pre-screening PSA/laboratory results
- 2. Administer Problem Assessment Scale of the Sexual Function Index (PAS-SFI)
- 3. Perform physical examination, including digital rectal exam, qualitative breast examination, height, weight, and vital signs blood pressure and pulse after 5 mins sitting
- 4. Obtain a 12-lead electrocardiogram (after 5 mins supine)
- Assess SAEs
- 6. Measure peak urinary flow (if required)
- 7. Measure post void residual volume (if required)

- 8. Measure prostate volume by transrectal ultrasound (TRUS) if suitable TRUS not available
- 9. Review inclusion/exclusion criteria, including concomitant medications, and confirm patient eligibility
- 10. Call RAMOS
- 11. Dispense placebo run-in medication and provide dosing instructions
- 12. Schedule next clinic visit

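### Partner pregnancies are to be collected until 6 months after the last dose, but no scheduled contact asks about them once dosing has stopped

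*Protocol*

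**What the plan says.** Section 7.4.5.1 sets the collection period: partner pregnancies "will be collected after the start of dosing until 6 months after the subject's last dose of study drug". Section 7.4.5 uses the same length of time for a different purpose. In countries whose local label calls for it, the recommendation is that the patient "avoids exposure of his partner to semen by use of a condom for 6 months after drug discontinuation".

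Section 3 gives the follow-up: "The total study duration for each subject will be up to 110 weeks, involving 11 scheduled visits". Visit 10, at week 104, is the end-of-treatment visit (Table 1, Appendix 2). Section 4.2.2 defines completion as run-in plus treatment, and section 10.5 ends the study at the final visit of the final subject.

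For men who stop treatment early, section 6.3 provides an end-of-treatment assessment and telephone calls every 6 months from baseline up to the 2-year anniversary of randomisation. The calls record death, AUR, BPH surgery or intervention, prostate cancer or biopsy, and outcomes of sexually related adverse events. The section then states: "No additional study activities other than those that are stated above are planned after a subject's permanent discontinuation from study treatment".

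Partner pregnancy is not listed at any visit in Table 1 or Appendix 2, nor in the end-of-treatment assessments of section 7.2.2.5.

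**The concern.** The protocol makes an unqualified promise to collect pregnancies over a period in which, for most men, nobody is scheduled to speak to the subject. For the rest, the scheduled call does not carry the question. After the last dose a pregnancy would be known only if the subject or his partner volunteered it.

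What is at stake is the reading of the safety data. If no post-dose pregnancies were reported, the sponsor could not tell whether none occurred or nobody asked. Section 7.4.2 also makes a spontaneous abortion in a partner a mandatory SAE, while section 7.4.7 ends SAE collection with the two-year study period. The two collection periods therefore do not match for an event the protocol treats as always serious.

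**Working it through.** **Inputs.** Screening interval: "Visit 1b should be conducted a maximum of 14 days after V1a" (Appendix 2), so 2 weeks. Run-in: "eligible subjects will receive placebo tamsulosin and placebo dutasteride for four weeks" (section 3), so 4 weeks. Treatment: 104 weeks (section 3). Sample size and discontinuation: 586 men and 20% (section 9.2.1). Allocation: 1:1 (section 5.4). Collection window: 6 months after the last dose, about 26 weeks (section 7.4.5.1).

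**Reproducing the plan's figure.** 2 + 4 + 104 = 110 weeks. Visits 1a, 1b and 2 to 10 make 11 visits. Both match section 3.

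**Completers.** Scheduled time after the last dose is 110 − (2 + 4 + 104) = 0 weeks, against about 26 needed. Covering the window would need 110 + 26 = 136 weeks. The ±14-day allowance at Visit 10 could add at most 2 weeks, and only if dosing had stopped at exactly week 104. Expected completers are 586 × 0.80 = 468.8, about 469.

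**Early discontinuers.** Expected number: 586 × 0.20 = 117.2, about 117. Calls fall at months 6, 12, 18 and 24. For a man who stops at month t, the window closes at t + 6, and the part lying before the last call is min(6, 24 − t) months:

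- t = 18 or earlier: 6 of 6 months
- t = 20: 4 of 6
- t = 22: 2 of 6

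So the calls reach the end of the window only for men who stop by month 18, and even then pregnancy is not a listed item.

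**Other post-dose contacts.** Section 4.2.1 follows men for up to 6 months, but only for sexual-function adverse events that led to withdrawal. Section 7.4.7 follows only adverse events still ongoing, and section 7.4.5.2 says pregnancy itself is not an adverse event. It also mentions a follow-up contact that no schedule defines. Section 7.4.5.2 follows a partner to outcome, but only once the pregnancy is known.

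**Number of men.** The protocol does not say how many have a partner of childbearing potential. Assume 1% to 10%. Across both arms that is 586 × 0.01 = 5.9 to 586 × 0.10 = 58.6, about 6 to 59 men. Only half receive dutasteride: 293 × 0.01 = 2.9 to 293 × 0.10 = 29.3, about 3 to 29 men. These are men with such a partner, not conceptions, and certainly not affected fetuses.

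**The case against.** The best defence is that collection was meant to be passive. Section 7.4.5.1 does not say that subjects will be questioned. Section 7.4.5.2 is triggered by a report, with a form due within 2 weeks of the site learning of a pregnancy. For SAEs arising from a post-study pregnancy it relieves the investigator of any duty to seek information. A reporting window without a visit is coherent on that view. This stands in part, but the key phrase in 7.4.5.2, which ties post-study pregnancy to 6 months after the last dose, can be read two ways. If it means within 6 months, it sits badly with an undertaking to collect all pregnancies in that period. If it means beyond 6 months, active collection inside the window is implied and nothing scheduled delivers it.

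Three stronger readings are tempting and are not supported:

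- A reader might infer that section 6.3 forbids the question, or that every contact ends with dosing. It omits the item and says no further activity is planned, which is not a prohibition. Some men do have further contact under sections 4.2.1 and 7.4.7.
- A reader might infer an established fetal risk with a 6-month duration. Section 7.4.5 describes harm to a male fetus as possible if the drug is given to the mother, and as unlikely through semen. The 6 months is a condom recommendation in some countries and a collection period, not a stated risk window.
- A reader might count all 6 to 59 men as exposed. Half the men receive dutasteride placebo.

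It is also fair that partner pregnancy is not among the safety endpoints in section 7.3.1 and has no planned analysis in section 9.3.7.2. The Study Procedures Manual, which is not at hand, might contain a contact procedure. However, section 7.4.8 refers to it for post-study AEs and SAEs and does not mention partner pregnancy.

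**Conclusion.** The point holds as a mismatch between a stated collection window and the contacts planned to serve it. Scheduled active ascertainment after the last dose is 0 of about 26 weeks for about 469 completers. For the roughly 117 early discontinuers no call lists the item, and for those stopping after month 18 the calls also end too soon. The counts rest on the protocol's own 20% discontinuation. The figure of about 3 to 29 dutasteride-treated men with a partner of childbearing potential rests on an assumed 1% to 10%.

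The consequence is confined to the completeness and reading of a small part of the safety data. Efficacy is untouched, spontaneous reports still count, and the protocol regards the harm by this route as unlikely. It is worth correcting because the correction is cheap, not because the expected number of events is large.

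**What to change.** Reconcile sections 3, 6.3, 7.4.5.1, 7.4.5.2, 7.4.7 and Table 1 so that they describe one collection period and one method. This is a data-collection change only and takes no position on contraception or treatment.

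1. In section 6.3, add partner pregnancy to the items asked at the existing biannual calls.
2. At Visit 10 and at the end-of-treatment assessment (section 7.2.2.5), ask about partner pregnancy and record whether there is a partner of childbearing potential. The second item is needed because no section now records it. Inclusion criterion 9 touches on it only in countries where the local monograph mandates condom use.
3. For men so recorded whose window runs past their last scheduled contact (completers and those stopping after month 18), choose one of two options. Either add one short telephone contact at the end of the window, or state in section 7.4.5.1 that collection after the study is by spontaneous report only, so that an absence of reports is not read as an absence of pregnancies.

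The cost is amendment wording, one question and one data item. If the call is chosen, existing site staff make a few short calls after the 110-week schedule, and the end-of-study definition in section 10.5 must be adjusted to allow for them. The question itself adds no contact for men who stop by month 18, because their calls already exist.
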